9.7.3.3 Power for composite renal endpoint

With an expected hazard reduction of 30% (LCZ696 over valsartan) in composite renal endpoint, an annual first occurrence of renal events rate of 0.63% (or 1%), an average follow-up of 3.375 years, and a two-sided alpha of 0.05, forty-six hundred patients will provide a power of 36% (or 52%). When the hazard reduction is about 35%, forty-six hundred patients will provide a power of 47% (or 66%) when the annual event rate is 0.63% (or 1%). Note that the power provided here is conditional power, when the null hypotheses for the primary endpoint, the secondary endpoints of KCCQ change and NYHA class change at month 8 are all rejected.

The power estimations are mainly based on data observed from recently completed PARADIGM-HF trial. In that trial, the observed annual event rate for composite renal endpoint is 0.63% and the hazard reduction of LCZ696 over enalapril is 37%.

9.7.3.4 Power for all-cause mortality

With a reduction of 20% in mortality, an annual all-cause mortality rate of 5% (25% increase from CV mortality), an average follow-up of 3.375 years, and a two-sided alpha of 0.05, forty-six hundred patients will provide a power of 81%. When the reduction is about 15%, forty-six hundred patients will provide a power of 56%.

10 Ethical considerations

10.1 Regulatory and ethical compliance

This clinical study was designed and shall be implemented and reported in accordance with the ICH Harmonized Tripartite Guidelines for Good Clinical Practice, with applicable local regulations (including European Directive 2001/20/EC, US Code of Federal Regulations Title 21, and Japanese Ministry of Health, Labor, and Welfare), and with the ethical principles laid down in the Declaration of Helsinki.

10.2 Informed consent procedures

Eligible patients may only be included in the study after providing written (witnessed, where required by law or regulation), Institutional Review Board/Independent Ethics Committee/Research Ethics Board (IRB/IEC) approved informed consent, or, if incapable of doing so, after such consent has been provided by a legally acceptable representative of the patient. In cases where the patient's representative gives consent, the patient should be informed about the study to the extent possible given his/her understanding. If the patient is capable of doing so, he/she should indicate assent by personally signing and dating the written informed consent document or a separate assent form. Informed consent must be obtained before conducting any study-specific procedures (i.e., all of the procedures described in the

protocol). The process of obtaining informed consent should be documented in the patient source documents.

Novartis will provide to investigators in a separate document a proposed informed consent form that complies with the ICH GCP guideline and regulatory requirements and is considered appropriate for this study. Any changes to the proposed consent form suggested by the investigator must be agreed to by Novartis before submission to the IRB/IEC, and a copy of the approved version must be provided to the Novartis monitor after IRB/IEC approval.

Women of child bearing potential should be informed that taking the study drug may involve unknown risks to the fetus if pregnancy were to occur during the study and agree that in order to participate in the study they must adhere to the contraception requirement for the duration of the study. If there is any question that the patient will not reliably comply, they should not be entered in the study.

This study includes an optional pharmacogenetic and pharmacogenomic component which requires a separate signature if the patient agrees to participate. It is required as part of this protocol that the Investigator presents this option to the patient at all participating sites where this component of the study is conducted. The process for obtaining informed consent should be exactly the same as described above for the main informed consent.

Declining to participate in pharmacogenetic and/or pharmacogenomic assessments will in no way affect the patient's ability to participate in the main research study.

In the event that Novartis wants to perform testing on the samples that are not described in this protocol, additional Institutional Review Board and/or ethics committee approval will be obtained.

10.3 Responsibilities of the investigator and IRB/IEC

The protocol and the proposed informed consent form must be reviewed and approved by a properly constituted Institutional Review Board/Independent Ethics Committee/Research Ethics Board (IRB/IEC) before study start. A signed and dated statement that the protocol and informed consent have been approved by the IRB/IEC must be given to Novartis before study initiation. Prior to study start, the investigator is required to sign a protocol signature page confirming his/her agreement to conduct the study in accordance with these documents and all of the instructions and procedures found in this protocol and to give access to all relevant data and records to Novartis monitors, auditors, Novartis Clinical Quality Assurance representatives, designated agents of Novartis, IRBs/IECs, and regulatory authorities as required. If an inspection of the clinical site is requested by a regulatory authority, the investigator must inform Novartis immediately that this request has been made.

10.4 Publication of study protocol and results

Novartis assures that the key design elements of this protocol will be posted in a publicly accessible database such as clinicaltrials.gov. In addition, upon study completion and finalization of the study report the results of this trial will be either submitted for publication and/or posted in a publicly accessible database of clinical trial results.

11 Protocol adherence

Investigators ascertain they will apply due diligence to avoid protocol deviations. Under no circumstances should the investigator contact Novartis or its agents, if any, monitoring the trial to request approval of a protocol deviation, as requests to approve deviations will not be granted.

This protocol defines the study objectives, the study procedures and the data to be collected on study participants. Under no circumstances should an investigator collect additional data or conduct any additional procedures for any research related purpose involving any investigational drugs.

If the investigator feels a protocol deviation would improve the conduct of the study this must be considered a protocol amendment, and unless such an amendment is agreed upon by Novartis and approved by the IRB/IEC it cannot be implemented. All significant protocol deviations will be recorded and reported in the CSR.

Laboratory values	
ALT or AST > 5 x ULN (with or without TBL > 2 x ULN [mainly conjugated fraction])
 
ALP > 5 x ULN (with or without TBL > 2 x ULN [mainly conjugated fraction])
 
TBL > 3 x ULN
 
Potential Hy's Law cases (defined as ALT/AST > 3 x ULN and TBL > 2 x ULN [mainly conjugated fraction] without notable increase in ALP to > 2 x ULN)

AEs	
Any clinical event of jaundice (or equivalent term)
 
ALT or AST > 3 x ULN accompanied by general malaise, fatigue, abdominal pain, nausea, or vomiting, or rash with eosinophilia
 
Any event that links to a preferred term (PT) in the MedDRA dictionary falling under the SMQ sub-module "Drug-related hepatic disorders – severe events only"* or any "Hy's law case" PT

* These events cover the following: hepatic failure, fibrosis and cirrhosis, and other liver damage-related conditions; the non-infectious hepatitis; the benign, malignant and unspecified liver neoplasms

Table 14-2 Liver event follow up requirements

Criteria	Event type	Actions required	Follow-up monitoring
Potential Hy's Law case ^a	Medically significant	
Discontinue the study drug immediately
 
Hospitalize, if clinically appropriate
 
Report to Novartis as an SAE
 
Establish causality
	
ALT, AST, TBL, Alb, PT, ALP and γGT until resolution^c (frequency at investigator discretion)

ALT or AST			
> 8 x ULN	Medically significant	
Repeat LFT within 48 hours
 
If elevation persists, discontinue the study drug immediately
 
Hospitalize if clinically appropriate
 
Report to Novartis as an SAE
 
Establish causality
	
ALT, AST, TBL, Alb, PT, ALP and γGT until resolution^c (frequency at investigator discretion)

> 5 to \leq 8 x ULN	Medically significant	
Repeat LFT within 48 hours
 
If elevation persists for more than 2 weeks, discontinue the study drug
 
Report to Novartis as an SAE
 
Establish causality
	
ALT, AST, TBL, Alb, PT, ALP and γGT until resolution^c (frequency at investigator discretion)

> 3 x ULN accompanied by symptoms ^b	Medically significant	
Discontinue the study drug immediately
 
Hospitalize if clinically appropriate
 
Report to Novartis as an SAE
 
Establish causality
	
ALT, AST, TBL, Alb, PT, ALP and γGT until resolution^c (frequency at investigator discretion)

> 3 to \leq 5 x ULN	AESI	Central laboratory to report to	Investigator discretion

Criteria	Event type	Actions required	Follow-up monitoring
(patient is asymptomatic)		Investigator & Novartis Repeat LFT once or twice in the week If elevation persists, establish causality	Monitor LFT within 1 to 4 weeks or at next visit
≤ 3 x ULN (patient is asymptomatic)	N/A	Repeat LFT at next visit	
ALP (isolated)			
> 5 x ULN	Medically significant	Repeat LFT within 48 hours If elevation persists, report to Novartis as an SAE Establish causality	Investigator discretion Monitor LFT within 1 to 4 weeks or at next visit
> 2 to ≤5 x ULN (patient is asymptomatic)	AESI	Central laboratory to report to Investigator & Novartis Repeat LFT once or twice in the week. If elevation persists, establish causality	Investigator discretion Monitor LFT within 1 to 4 weeks or at next visit
≤ 2 x ULN (patient is asymptomatic)	N/A	Repeat LFT at next visit	
TBL (isolated)			
> 3 x ULN	Medically significant	Repeat LFT within 48 hours If elevation persists, discontinue the study drug immediately Hospitalize if clinically appropriate Report to Novartis as an SAE Establish causality	ALT, AST, TBL, Alb, PT, ALP and γGT until resolution ^c (frequency at investigator discretion) Test for hemolysis (e.g., reticulocytes, haptoglobin, unconjugated [indirect] bilirubin)
> 1.5 to ≤ 3 x ULN (patient is asymptomatic)	AESI	Central laboratory to report to Novartis Repeat LFT once or twice in the week. If elevation persists, establish causality	investigator discretion Monitor LFT within 1 to 4 weeks or at next visit
≤ 1.5 x ULN (patient is asymptomatic)	N/A	Repeat LFT at next visit	
Preferred terms			
Jaundice	Medically significant	Discontinue the study drug immediately Hospitalize the patient Report to Novartis as an SAE Establish causality	ALT, AST, TBL, Alb, PT, ALP and γGT until resolution ^c (frequency at investigator discretion)
"Drug-related hepatic	Medically significant	Discontinue the study drug hospitalization if clinically	Investigator discretion

Criteria	Event type	Actions required	Follow-up monitoring
disorders - severe events only" SMQ AE		appropriate Report to Novartis as an SAE Establish causality	

^a Elevated ALT/AST > 3 x ULN and TBL > 2 x ULN but with no notable increase in ALP to > 2 x ULN

^b General malaise, fatigue, abdominal pain, nausea, or vomiting, rash with eosinophilia

^c Resolution is defined as an outcome of one of the following: return to baseline values, stable values at three subsequent monitoring visits at least 2 weeks apart, remain at elevated level after a maximum of 6 months, liver transplantation, and death.

15 Appendix 3: Treatment guidelines for hyperkalemia (serum potassium greater than or equal to 5.3 mmol/L [mEq/L])

General principles

Elevation of potassium levels above the predefined values should be repeated and confirmed before any action is taken.

Any patient with a serum potassium > 5.3 mmol/L (mEq/L) at any time after randomization requires the Investigator to confirm the potassium concentration in a non-hemolyzed sample via an immediate repeat lab sample to both the clinic local lab and the study central lab. Regular, repeated checks of potassium concentration (beyond that prescribed in the protocol) should continue until it is clear that the potassium concentration is stable and not rising into the range of concern (≥ 5.5 and < 6.0 mmol/L [mEq/L]) or potential danger (≥ 6.0 mmol/L [mEq/L]).

Patients with elevated potassium value will be managed according to the corrective actions outlined below. Hyperkalemia should be followed until resolution.

Corrective action for management of hyperkalemia

Serum potassium greater than 5.3 and less than or equal to 5.5 mmol/L (mEq/L)

- Confirm potassium concentration in a non-hemolyzed sample
- Reinforce low potassium diet and restriction of food/drinks with high potassium content (e.g. orange juice, melon, bananas, tomatoes, dried fruits, potatoes, low-salt substitutes, tomatoes, coffee, etc.)
- Correct metabolic acidosis if necessary.
- Review medical regimen (including dietary supplements and over-the-counter medications) for agents known to cause hyperkalemia. Consider reduction in dose or discontinuation of these agents:
 - MRAs (if they are believed to be the most likely cause of hyperkalemia)
 - Potassium-sparing diuretics (e.g. amiloride and triamterene) including in combination products with thiazide or loop diuretics
 - Potassium supplements, e.g., potassium chloride
 - Salt substitutes

- Non-steroidal anti-inflammatory drugs (NSAIDs)
- Cyclo-oxygenase-2 (COX-2) inhibitors
- Trimethoprim and trimethoprim-containing combination products, such as Bactrim[®] and Septra[®] (trimethoprim/sulfamethoxazole fixed combination)
- Herbal Supplements:
 - For example, Noni juice, alfalfa (*Medicago sativa*), dandelion (*Taraxacum officinale*), horsetail (*Equisetum arvense*), nettle (*Urtica dioica*), milkweed, lily of the valley, Siberian ginseng, hawthorn berries
- Assess patient for dehydration or any condition that could lead to dehydration (e.g., diarrhea, vomiting) and/or hypovolemia and initiate appropriate corrective measures of rehydration.
- Repeat serum potassium measurement within 3 to 5 days
- If serum potassium remains > 5.3 and ≤ 5.5 mmol/L (mEq/L), regularly monitor serum potassium levels to ensure stability (suggested once monthly)
- Consider down-titration of study drug, according to investigator's medical judgment.

Serum potassium greater than 5.5 and less than 6.0 mmol/L (mEq/L)

- Confirm potassium concentration in a non-hemolyzed sample
- Consider down-titration or temporarily discontinue study drug according to investigator medical judgment.
- Apply all measures outlined for serum potassium > 5.3 and ≤ 5.5 mmol/L
- Repeat serum potassium measurement after 2-3 days
- If serum potassium < 5.5 mmol/L, consider resumption of study drug at lower dose with repeat potassium within 5 days

Serum potassium greater than or equal to 6.0 mmol/L (mEq/L)

- Immediately discontinue study drug
- Confirm potassium concentration in a non-hemolyzed sample
- Urgently evaluate patient and treat hyperkalemia as clinically indicated
- Apply all measures outlined for serum potassium > 5.3 and < 6.0 mmol/L (mEq/L)

No resumption of study drug without individualized case discussion with and permission from Novartis medical monitor or his/her designee.

16 Appendix 4: Guidelines for the management of blood pressure

Guidelines

1. Investigator should monitor BP closely
2. If symptomatic hypotension occurs:
 - a. Correct any treatable cause, e.g. hypovolemia

- b. If hypotension persists, any antihypertensive drug such as diuretics, calcium channel blockers (CCBs), nitrates, beta blockers, aldosterone antagonists and α -blockers, should be down-titrated or stopped first before down-titration of the study drug is considered. Any non-antihypertensive drug (such as nitrates) should be considered for down-titration prior to study drug as determined by the best judgment of the investigator.
- c. If hypotension persists, the study drug should be down-titrated or even temporarily withdrawn. The dose re-challenge and medications adjust guidelines described in [Section 5.5.5](#) should be adhered to as much as possible.

17 Appendix 5: Guidelines for the management of renal dysfunction

General principles:

Glomerular filtration rate in HF patients depends on intrinsic renal function and on a balance between afferent and efferent glomerular arterial tonicity. This tonicity is partly regulated by a stimulation of angiotensin II and could be affected by either study drug. Moreover, renal dysfunction may develop or may deteriorate in some patients after study drug administration. These recommendations have been developed to guide the investigators in managing patients with renal dysfunction after randomization.

Two types of response to serum creatinine increase are described:

Surveillance situation

If, at any time after randomization, eGFR decreases by $\geq 25\%$ from baseline (Visit 1) (or if serum creatinine concentration increase to 2.5 mg/dL [221 $\mu\text{mol/L}$]), the investigator will check for potentially reversible causes of renal dysfunction such as:

- Non-steroidal anti-inflammatory drug intake, antibiotics, or other treatments known to affect creatinine
- Volume decrease, including that resulting from excessive dosing of diuretics
- Urinary infection
- Urinary tract obstruction
- Study drug

Action situation

If a patient's eGFR decreases by $\geq 40\%$ from baseline (Visit 1) (or if serum creatinine concentration rises above 3 mg/dL (265 $\mu\text{mol/L}$)), the investigator will check for potentially reversible causes of renal dysfunction (see above).

The investigator may consider down-titration of study drug. If the investigator judges that study drug has to be stopped, he/she will have to contact the Novartis medical monitor or his/her designee. Thereafter, serum creatinine assessments will have to be repeated at least

each week until levels return to acceptable values. If study drug was stopped, every effort will be done to restart it again, according to clinical conditions.

18 Appendix 6: Blood log for PK sample collection

Visit	Visit name	Timepoint	Volume	Sample Number	Dose reference ID
199	Treatment run in	Predose	2 mL	1	1
203 ^a	Week 16	0 hours pre-dose	2 ml	2	2
203 ^b	Week 16	0.5 - 2 hours post-dose	2 ml	3	2
203 ^c	Week 16	3-5 hours post-dose	2 ml	4	2
205 ^a	Week 48	0 hours pre-dose	2 ml	5	3
205 ^b	Week 48	0.5 - 2 hours post-dose	2 ml	6	3
205 ^c	Week 48	3 - 5 hours post-dose	2 ml	7	3

a, b, c: If the samples are not collected at Visit 203, the samples at the same time points can be collected at Visit 205

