7.1 Adverse events

An AE is any untoward medical occurrence (i.e., any unfavorable and unintended sign [including abnormal laboratory findings], symptom or disease) in a subject or clinical investigation subject after providing written informed consent for participation in the study. Therefore, an AE may or may not be temporally or causally associated with the use of a medicinal (investigational) product.

An untoward medical occurrence may be a study endpoint as well as meeting the definition for an AE. Specific guidance on the appropriate recording and reporting of events that meet the criteria for both a study endpoint and an AE are provided in [Section 7.3](#).

The occurrence of AEs should be sought by non-directive questioning of the patient at each visit during the study. AEs also may be detected when they are volunteered by the patient during or between visits or through physical examination, laboratory test, or other assessments.

Abnormal laboratory values or test results constitute AEs only if they fulfill at least one of the following criteria:

- they induce clinical signs or symptoms,
- they are considered clinically significant,

- they require therapy.

Clinically significant abnormal laboratory values or test results should be identified through a review of values outside of normal ranges/clinically notable ranges, significant changes from baseline or the previous visit, or values which are considered to be non-typical in patient with underlying disease. Investigators have the responsibility for managing the safety of individual patient and identifying AEs. Alert ranges for labs and other test abnormalities are included in [Appendix 1](#).

AEs should be recorded in the AE CRF under the signs, symptoms or diagnosis associated with them accompanied by the following information.

- the severity grade
 - mild: usually transient in nature and generally not interfering with normal activities
 - moderate: sufficiently discomforting to interfere with normal activities
 - severe: prevents normal activities
- its relationship to the study treatment (no/yes)
- its duration (start and end dates) or if the event is ongoing an outcome of not recovered/not resolved should be reported.
- whether it constitutes an SAE
- action taken regarding study treatment
- whether other medication or therapies have been taken (concomitant medication/non-drug therapy)

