7.2 Serious adverse event reporting

To ensure patient safety all SAEs, regardless of causality, occurring after the patient has provided informed consent and until 30 days after the last study visit must be reported to Novartis within 24 hours of learning of its occurrence.

At a minimum, patients will be contacted for safety evaluations during the 30 days following the last study visit or following the last administration of study drug, including a final contact at the 30-day point. Documentation of attempts to contact the patient should be recorded in the source documentation. Furthermore, under this category, SAEs experienced after the 30 days period should only be reported to Novartis if the investigator suspects a causal relationship to study treatment.

Recurrent episodes, complications, or progression of the initial SAE must be reported as follow-up to the original episode, regardless of when the event occurs. This report must be

submitted within 24 hours of the investigator receiving the follow-up information. An SAE that is considered completely unrelated to a previously reported one should be reported separately as a new event.

Follow-up information provided should describe whether the event has resolved or continues, if and how it was treated, whether the treatment code was broken or not and whether the patient continued or withdrew from study participation. Each re-occurrence, complication, or progression of the original event should be reported as a follow-up to that event regardless of when it occurs.

If the SAE is not previously documented in the Investigator's Brochure (new occurrence) and is thought to be related to the investigational treatment, a Novartis Drug Safety and Epidemiology Department associate may urgently require further information from the investigator for Health Authority reporting. If the SAE is considered Suspected Unexpected Serious Adverse Reactions (SUSARs), Novartis may need to issue an Investigator Notification (IN) to inform all investigators involved in any study with the same investigational treatment that this SAE has been reported. All SUSARs will be collected and reported to the competent authorities and relevant ethics committees (ECs) in accordance with Directive 2001/20/EC or as per national regulatory requirements in participating countries.

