7.3.3 Exploratory endpoints and other SAEs that meet the definition of SUSARs

Exploratory endpoints that meet SUSAR criteria, and all other SAEs that do not meet the criteria in Section 7.3.1 and Section 7.3.2 but do meet SUSAR criteria will be unblinded and reported to regulatory agencies, ECs, or investigators during the study.

Monitoring of safety data by the Data Monitoring Committee

An external independent Data Monitoring Committee (DMC) (Section 8.4) will be appointed to monitor the safety of study participants and to ensure that the program is being conducted with highest scientific and ethical standards. This DMC will review the endpoint and SAE data throughout the trial in a semi-unblinded manner. Should the DMC make recommendations on the conduct of the trial that are considered to have significant bearing on the benefit-risk of the trial, these will be communicated by Novartis to HAs, ECs and investigators within an appropriate timeframe and implement any additional actions required.

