7.4 Liver safety monitoring

To ensure patient safety and enhance reliability in determining the hepatotoxic potential of an investigational drug, a standardized process for identification, monitoring and evaluation of liver events has to be followed.

Liver events are divided into two categories:

- Liver events of special interest (AESI) which consist of LFT elevations
- Medically significant liver events which are considered as SAEs and which consist of marked elevations of LFTs and / or pre-specified AEs.

Please refer to [Table 14-1](#) in [Appendix 2](#) for complete definitions of liver events.

Any liver event which meets the criteria for “**medically significant**” event as outlined in [Table 14-1](#) of [Appendix 2](#) should follow the **standard procedures for SAE reporting** as described in [Section 7.2](#).

Every liver event as defined in [Table 14-1](#) of [Appendix 2](#) should be followed up by the investigator or designated personnel at the trial site as summarized below. Detailed information is outlined in [Table 14-2](#) in [Appendix 2](#).

- Repeating the LFT to confirm elevation as appropriate
- Discontinuation of the investigational drug if appropriate
- Hospitalization of the patient if appropriate
- A causality assessment of the liver event via exclusion of alternative causes (e.g., disease, co-medications)
- An investigation of the liver event which needs to be followed until resolution.

These investigations can include serology tests, imaging and pathology assessments, hepatologist’s consultancy, based on investigator’s discretion. All follow-up information, and the procedures performed should be recorded on appropriate CRF pages, including the liver event overview CRF pages.

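### Protocol Appendix 2 gives two SAE reporting rules for an isolated ALP above 5 x ULN: report on the first value, or report only if a repeat test confirms it

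*Protocol*

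**What the plan says.** Four places in the protocol bear on an isolated ALP above 5 x ULN.

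- **Appendix 2, Table 14-1** lists it among the laboratory criteria for a medically significant event (SAE): "ALP > 5 x ULN (with or without TBL > 2 x ULN [mainly conjugated fraction"]). The words on bilirubin bring an isolated rise into the definition. No confirming repeat is required.
- **Section 7.4** describes the second of its two liver categories as "Medically significant liver events which are considered as SAEs and which consist of marked elevations of LFTs" or pre-specified AEs. It sends any event meeting the Table 14-1 criteria to the standard SAE procedure in Section 7.2. Separately, it lists follow-up steps, the first being "Repeating the LFT to confirm elevation as appropriate", and refers to Table 14-2 for their detail.
- **Section 7.2** says that all SAEs, regardless of causality, "must be reported to Novartis within 24 hours of learning of its occurrence".
- **Appendix 2, Table 14-2**, row for isolated ALP > 5 x ULN, also carries the label medically significant. Its actions are a repeat LFT within 48 hours, then "If elevation persists, report to Novartis as an SAE", then a causality assessment.

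**The concern.** The first three texts make the initial value reportable. The fourth makes the report depend on a second value. A site can comply with one rule and breach the other, and the protocol gives no order of precedence.

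What is at stake is consistency of safety reporting. SAE reports feed the DMC (Section 7.3.3: "This DMC will review the endpoint and SAE data throughout the trial in a semi-unblinded manner") and the SAE summaries in SAP Section 10.3. Two careful sites could file different numbers of SAEs for the same laboratory finding, or file the same SAE at different times against a fixed deadline.

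**Working it through.** No sample size, power or alpha is involved. The check is a side-by-side reading, a row count and a comparison of clocks.

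**1. The two rules**

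| | Table 14-1 with 7.4 and 7.2 | Table 14-2, isolated ALP row |
|---|---|---|
| Label | Medically significant (SAE) | Medically significant |
| Trigger for the report | First value > 5 x ULN | Elevation that persists on repeat |
| Time allowed | 24 h from learning of it | Repeat within 48 h, then report |
| Value not confirmed | 1 SAE report | 0 SAE reports |
| Value persists | 1 SAE report | 1 SAE report, possibly later |

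**2. Does other text settle it?**

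- The Section 7.4 bullet on repeating the LFT is a follow-up step for an event already defined. It does not suspend the report.
- Section 7.1 restricts when a laboratory finding is an AE at all ("Abnormal laboratory values or test results constitute AEs only if they fulfill at least one of the following criteria"). Section 7.4, however, classes these liver events as SAEs directly.
- Section 6.5.4 points the same way as 7.4: a laboratory abnormality that meets a seriousness category goes to rapid SAE notification.

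**3. Is the ALP row like its neighbours?** Table 14-2 has 8 medically significant rows.

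| Row | Drug stop instruction | SAE report worded as conditional |
|---|---|---|
| Potential Hy's Law | Yes | No |
| ALT/AST > 8 x ULN | Yes, if it persists | No |
| ALT/AST > 5 to 8 x ULN | Yes, if it persists more than 2 weeks | No |
| ALT/AST > 3 x ULN with symptoms | Yes | No |
| Isolated ALP > 5 x ULN | None | **Yes** |
| Isolated TBL > 3 x ULN | Yes, if it persists | No |
| Jaundice | Yes | No |
| Severe drug-related hepatic disorder (SMQ) | Yes | No |

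The report is worded as conditional in 1 row and as a separate item in 8 − 1 = 7. Three of those seven also ask for a repeat within 48 hours, but there the persistence clause belongs to stopping the drug. The ALP row is also the only one without a drug stop, so a lighter rule may have been intended.

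**4. Timing for a persistent value**

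- Both clocks counted from when the site learns of the first value: latest repeat 48 h, deadline 24 h, so 48 − 24 = 24 h past the deadline with zero turnaround. An early repeat with a fast result can still meet 24 h, so lateness is possible, not certain.
- Clock started instead at the repeat result: the report can come up to 48 + 24 = 72 h after the first value is known, plus turnaround.

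The documents give no turnaround for a repeat LFT, so none is added. The figure of up to 72 hours in Section 3.1 concerns screening tests.

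**The case against.** The strongest reply is that Table 14-2 has a dedicated row for isolated ALP, that Section 7.4 refers sites to that table, and that a specific instruction can qualify a general one. On that reading only a cross-reference is missing. It does not stand: Section 7.4 uses Table 14-1 to define the SAE and Table 14-2 to follow up events already so defined, and it routes every event meeting the Table 14-1 criteria to Section 7.2.

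Other points carry some weight.

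- **The 24-hour overrun assumes that the first value starts the clock.** If the reportable occurrence is the confirmed elevation, nothing is late. This is fair: the overrun follows from the same conflict and is not a second, independent harm.
- **The 7-of-8 count is a reading.** In the ALT/AST > 8 and TBL > 3 rows the report follows a persistence clause on an earlier line, and the extracted text has lost any indentation. The count rests on the wording, since only the ALP row joins condition and report in one instruction. The mismatch with Table 14-1 does not depend on it.
- **The sponsor sees the values anyway.** Section 6.5.4 sends central laboratory results to the sponsor, and SAP Table 10-2 counts ALP > 5 x ULN from laboratory data. This limits the effect but does not remove the conflict.
- **The effect on the DMC is not shown.** Its data flow is set in a charter that is not among the documents. That stands; all that can be said is that its review includes SAE data.
- **The fix may come late.** The SAP sets the analysis cut-off at 30 April 2019, so a change may no longer alter what sites report.

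**Conclusion.** The concern holds. Two current protocol rules contradict each other on whether, and when, an isolated ALP above 5 x ULN is reported as an SAE.

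For each unconfirmed value the difference is one SAE report against none. For each persistent value it is a possible delay of up to 24 hours beyond the Section 7.2 deadline, on the assumption that the deadline runs from the first value and before any turnaround. The number of patients affected cannot be given, because the documents state no frequency for this finding.

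The importance is low. No drug stop, efficacy analysis, sample size or alpha depends on it, and no bias between arms is claimed. It is worth correcting because the duty to report has a fixed deadline and the correction is small.

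**What to change.** **Option A (preferred; agrees with Table 14-1, Sections 7.4 and 7.2, and the wording of the other seven rows).** In the isolated ALP > 5 x ULN row of Table 14-2, delete the persistence condition so that the instruction is simply to "report to Novartis as an SAE". Keep the 48-hour repeat and the causality assessment. The cost is one table cell, by amendment or site clarification letter. The downside is some extra SAE reports for elevations that are not confirmed.

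**Option B (if confirmation was intended for isolated ALP).** Keep the Table 14-2 row. In the Table 14-1 entry, add that an isolated value must be confirmed on repeat. In Section 7.4, add: *For isolated ALP > 5 x ULN, the 24-hour period in Section 7.2 starts when the site learns of the confirming repeat result.* The cost is one table entry and one sentence. The downside is that unconfirmed values appear only in the laboratory tables.

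Neither option adds a test or a visit. If amendment is no longer practical, a statement of which rule was applied would let readers interpret the SAE counts.
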